## Section 2 EuroQol by interview

Is patient able to complete Euroqol by interview?

Yes1	CARRY OUT EUROQOL INTERVIEW
No2	COMPLETE SECTION 3

**ASK** *We will also be asking you to fill in a short questionnaire 1-month after you were admitted to hospital. Do you think you will be able to complete a postal questionnaire at this time or will you have someone who can help you with this?* 

Yes.....1 No.....2

ASK Can we carry out this interview by telephone?

Yes.....1 No.....2

## Section 3 EuroQol by Proxy

Can you identify a suitable proxy to complete the EuroQol?

Yes1	GIVE PROXY FORM TO PROXY
No2	Subject has no EuroQol response

## 7-Day follow up EuroQol

Date of interview: \_\_\_/\_\_/

Interviewer Name: \_\_\_\_\_

Has patient been discharged?

Yes1	ENSURE PATIENT HAD SELF COMPLETE EUROQOL GIVEN TO THEM ON DISCHARGE, IF NOT POST SELF- COMPLETION EUROQOL TO PATIENT
No2	CARRY OUT INTERVIEW
Is patient unconscious?	
Yes1	DISCONTINUE INTERVIEW
No2	

IF PATIENT IS ABLE TO RESPOND TO INTERVIEWER ASK: Hello. Thank you for agreeing to take part in this study. We are interested in how you feel today. To find this out we would like you to fill in a short questionnaire. Do you feel able to complete this questionnaire *yourself?* 

Is patient able to self-complete Eurogol?

No.....2

## Yes.....1 GIVE PATIENT SELF COMPLETE EUROQOL AND ATTACH COMPLETED FORM TO BACK OF THIS FORM **COMPLETE SECTION 2**

IF A PROXY INTERVIEW HAS BEEN USED FOR BASELINE AND THE SUBJECT IS ABLE TO GIVE EUROQOL RESPONSES (EITHER BY SELF-COMPLETION OR **INTERVIEW) THEN PLEASE ENSURE THAT A PROXY INTERVIEW IS ALSO COMPLETED (IF POSSIBLE)** 

## Section 2 EuroQol by interview

Is patient able to complete euroqol by interview?

Yes1	CARRY OUT EUROQOL INTERVIEW
No2	COMPLETE SECTION 3

## Section 3 EuroQol by Proxy

Can you identify a suitable proxy to complete the EuroQol? IF PROXY IS USED AND IF A PROXY WAS USED FOR THE BASELINE INTERVIEW THEN ENSURE THAT SAME PROXY IS USED FOR FOLLOW UP.

Yes1	GIVE PROXY FORM TO PROXY
No2	Subject has no EuroQol response

## **28-Day follow up EuroQol**

Date of interview: \_\_\_/\_\_\_/

Interviewer Name: \_\_\_\_\_

Has patient been discharged?

Yes1	ENSURE PATIENT HAD SELF COMPLETE EUROQOL GIVEN TO THEM ON DISCHARGE, IF NOT POST SELF- COMPLETION EUROQOL TO PATIENT
No2	CARRY OUT INTERVIEW
Is patient unconscious?	
Yes1	DISCONTINUE INTERVIEW
No2	

IF PATIENT IS ABLE TO RESPOND TO INTERVIEWER ASK: Hello. Thank you for

agreeing to take part in this study. We are interested in how you feel today. To find this out we would like you to fill in a short questionnaire. Do you feel able to complete this questionnaire yourself?

Is patient able to self-complete EuroQol?

Yes1	
No2	

## GIVE PATIENT SELF COMPLETE EUROQOL AND ATTACH COMPLETED FORM TO BACK OF THIS FORM COMPLETE SECTION 2

IF A PROXY INTERVIEW HAS BEEN USED FOR BASELINE AND/OR 7-DAY INTERVIEW AND THE SUBJECT IS ABLE TO GIVE EUROQOL RESPONSES (EITHER BY SELF-COMPLETION OR INTERVIEW) THEN PLEASE ENSURE THAT A PROXY INTERVIEW IS ALSO COMPLETED (IF POSSIBLE)

#### Section 2 EuroQol by interview

Is patient able to complete EuroQol by interview?

Yes1	CARRY OUT EUROQOL INTERVIEW
No2	COMPLETE SECTION 3

## Section 3 EuroQol by Proxy

Can you identify a suitable proxy to complete the EuroQol? IF PROXY IS USED AND IF A

## PROXY WAS USED FOR THE BASELINE INTERVIEW THEN ENSURE THAT SAME PROXY IS USED FOR FOLLOW UP.

Yes1	GIVE PROXY FORM TO PROXY
No2	Subject has no EuroQol response

## Self completion Health Questionnaire

(English version for the UK) (validated for use in Eire)

Name		Study Number
Admission date	//	
Date of interview	·//	
Baseline 7-Day 28-Day	1 2 3	

By placing a tick in one box in each group below, please indicate which statements best describe your own health state today.

## **Mobility** I have no problems in walking about I have some problems in walking about I am confined to bed Self-Care I have no problems with self-care I have some problems washing or dressing myself I am unable to wash or dress myself Usual Activities (e.g. work, study, housework, family or leisure activities) I have no problems with performing my usual activities I have some problems with performing my usual activities I am unable to perform my usual activities Pain/Discomfort I have no pain or discomfort I have moderate pain or discomfort I have extreme pain or discomfort Anxiety/Depression I am not anxious or depressed I am moderately anxious or depressed I am extremely anxious or depressed

To help people say how good or bad a health state is, we have drawn a scale (rather like a thermometer) on which the best state you can imagine is marked 100 and the worst state you can imagine is marked 0.

We would like you to indicate on this scale how good or bad your own health is today, in your opinion. Please do this by drawing a line from the box below to whichever point on the scale indicates how good or bad your health state is today.

> Your own health state today

0

## **Health Questionnaire**

## English version for the UK

## SCRIPT FOR INTERVIEW ADMINISTRATION

Name:		Study Number:
Admission date:	//	
Date of interview:	//	
Name of interviewer:		
Baseline 7-Day 28-Day	1 2 3	

## GENERAL INTRODUCTION

## ONLY SECTIONS IN ITALICS ARE TO BE READ OUT

It is suggested that the administrator follows the script of the EQ-5D. Although allowance should be made for the interviewer's particular style of speaking, the wording of the questionnaire instructions should be followed as closely as possible. In the case of the EQ-5D descriptive system on page 2, the precise wording must be followed.

It is recommended that the administrator has a copy of the EQ-5D in front of him or her as it is administered over the telephone. This enables the respondent's answers to be entered directly on the EQ-5D by the administrator on behalf of the respondent (i.e. the appropriate boxes on page 3 are marked and the scale on page 4 is marked at the point indicating the respondents 'own health state today'). If the respondent asks for clarification, the administrator can help by re-reading the question verbatim. The administrator should not try to offer his or her own explanation but suggest that the respondent uses his or her own interpretation.

If the respondent has difficulty with regard to which box to mark, the administrator should repeat the question verbatim and ask the respondent to answer in a way that most closely resembles his or her thoughts about his or her health state today.

We are trying to find out what you think about your health. I will ask you a few brief and simple questions about your own health state today. I will explain the tasks fully as I go along but please interrupt me if you do not understand something or if things are not clear to you. Please also remember that there are no right or wrong answers. We are interested here only in your personal view.

First I am going to read out some questions. Each question has a choice of three answers. Please tell me which answer best describes your own health state today.

Do not choose more than one answer in each group of questions.

NOTE FOR INTERVIEWER: IT MAY BE NECESSARY TO REMIND THE RESPONDENT REGULARLY THAT THE TIMEFRAME IS TODAY. IN ALL CASES PLEASE INDICATE RESPONSES BY CIRCLING ONE NUMBER ONLY FOR EACH QUESTION.

## Mobility

First I'd like to ask you about mobility. Would you say you have...

- 1. No problems in walking about?
- 2. *Some problems in walking about?*
- 3. *Are you confined to bed?*

#### Self-Care

Next I'd like to ask you about self-care. Would you say you have...

- 1. No problems with self-care?
- 2. Some problems washing or dressing yourself?
- 3. *Are you unable to wash or dress yourself?*

#### **Usual Activities**

Next I'd like to ask you about usual activities, for example work, study, housework, family or leisure activities. Would you say you have: ...

- 1. No problems with performing your usual activities?
- 2. Some problems with performing your usual activities?
- 3. Are you unable to perform your usual activities?

## **Pain/Discomfort**

Next I'd like to ask you about pain or discomfort. Would you say you have...

- 1. No pain or discomfort?
- 2. *Moderate pain or discomfort?*
- 3. *Extreme pain or discomfort?*

## **Anxiety/Depression**

Finally I'd like to ask you about anxiety or depression. Would you say you are...

- 1. Not anxious or depressed?
- 2. *Moderately anxious or depressed?*
- 3. *Extremely anxious or depressed?*

I would now like to ask you to do a rather different task.

To help you say how good or bad your health state is, I'd like you to try to picture in your mind a scale that looks a bit like a thermometer. Can you do that? The best health state you can imagine is marked 100 (one hundred) at the top of the scale and the worst state you can imagine is marked 0 (zero) at the bottom.

I would now like you to tell me the point on this scale where you would put your own health state today.

Your own health state today

# Health Questionnaire

# English version for the UK

# Script for proxy version of the EQ-5D

(Asking the proxy to rate how he or she, (i.e. the proxy), would rate the subject's health)

Name:	Study Number
Date on which questionnaire was completed	(dd/mm/yy) / /
Name of person filling in this questionnaire:	
Relationship to patient:	

#### Proxy version of the EQ-5D:

By placing a tick in one box in each group below, please indicate which statements best describe \_\_\_\_\_\_\_health state today.

Do not tick more than one box in each group

# Mobility

No problems in walking about	
Some problems in walking about	
Confined to bed	
Self-Care	
No problems with self-care	
Some problems washing or dressing himself/herself	
Unable to wash or dress himself/herself	
Usual Activities (e.g. work, study, housework, family or leisure activities)	
No problems with performing his/her usual activities	
Some problems with performing his/her usual activities	
Unable to perform his/her usual activities	
Pain/Discomfort	
No pain or discomfort	
Moderate pain or discomfort	
Extreme pain or discomfort	
Anxiety/Depression	
Not anxious or depressed	
Moderately anxious or depressed	
Extremely anxious or depressed	

To help people say how good or bad a health state is, we have drawn a scale (rather like a thermometer) on which the best state you can imagine is marked 100 and the worst state you can imagine is marked 0.

We would like you to indicate on this scale how good or bad

health is today, in your opinion. Please do this by drawing a line from the box below to whichever point on the scale indicates how good or bad you think the subject's health state is today.

Health today

Best imaginable health state

Worst imaginable health state

# A RANDOMISED CONTROLLED TRIAL TO EVALUATE IMPACT OF DIAGNOSTIC TESTING FOR INFLUENZA, RESPIRATORY SYNCYTIAL VIRUS AND STREPTOCOCCUS PNEUMONIAE INFECTION ON THE MANAGEMENT OF ACUTE ADMISSIONS IN THE ELDERLY AND HIGH-RISK ADULTS.

Name \_\_\_\_\_

Study Number \_\_\_\_\_

Self completion Health Questionnaire (Day 7 Postal) (English version for the UK) (validated for use in Eire)

We would like to thank you again for agreeing to take part in the above study. As part of this research we are interested in your health today. For this reason we would like you to complete the following short questionnaire and return it to us in the pre-paid envelope provided. We would be grateful if you could complete this questionnaire as soon as possible. Please return it to us in the pre-paid envelope provided.

Please indicate the date on which you completed this questionnaire:

Date: \_\_\_/\_\_/

By placing a tick in one box in each group below, please indicate which statements best describe your own health state today.

Mobility	
I have no problems in walking about	
I have some problems in walking about	
I am confined to bed	
Self-Care	
I have no problems with self-care	
I have some problems washing or dressing myself	
I am unable to wash or dress myself	
Usual Activities ( e.g. work, study, housework, family or leisure activities )	
I have no problems with performing my usual activities	
I have some problems with performing my usual activities	
I am unable to perform my usual activities	
Pain/Discomfort	
I have no pain or discomfort	
I have moderate pain or discomfort	
I have extreme pain or discomfort	
Anxiety/Depression	
I am not anxious or depressed	
I am moderately anxious or depressed	
I am extremely anxious or depressed	

Best imaginable health state

To help people say how good or bad a health state is, we have drawn a scale (rather like a thermometer) on which the best state you can imagine is marked 100 and the worst state you can imagine is marked 0.

We would like you to indicate on this scale how good or bad your own health is today, in your opinion. Please do this by drawing a line from the box below to whichever point on the scale indicates how good or bad your health state is today.

> Your own health state today

imaginable health state

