The costs of performing rapid molecular and near patient diagnostic tests for influenza, RSV and S. pneumoniae infections, differ significantly from the cost of traditional laboratory culture.

6. Assess cost-savings associated with earlier use of narrow-spectrum antimicrobial therapy (or avoidance or discontinuation of antibiotics) in patients whose influenza, RSV and *S. pneumoniae* infections are diagnosed more rapidly by rapid molecular and near patient diagnostic tests, in comparison to traditional laboratory culture.

The earlier use of narrow-spectrum antimicrobial therapy (or avoidance or discontinuation of antibiotics) in patients whose influenza, RSV and S. pneumoniae infections are diagnosed more rapidly by rapid molecular and near patient diagnostic tests results in significant cost-savings, in comparison to traditional laboratory culture.

7. Compare the outcome of patients whose influenza, RSV, and *S. pneumoniae* is diagnosed more rapidly by rapid molecular and near patient diagnostic tests, compared to those who are diagnosed by traditional laboratory culture.

A streamlining of antimicrobial prescribing that may arise from more rapid diagnosis of influenza, RSV and S. pneumoniae infections by rapid molecular and near patient diagnostic tests does not adversely affect patient outcome.

8. Assess the impact that rapid molecular and near patient diagnostic tests have on the costs associated with an inpatient stay and on costs post-discharge up to a maximum of 28 days after admission.

Any increase in costs incurred by rapid molecular and near patient diagnostic tests, in comparison to traditional laboratory culture, is more than offset by savings that arise from either rational antimicrobial prescribing or earlier discharge from the hospital.

9. To assess the impact that rapid molecular and near patient diagnostic tests have on quality-of-life, as measured by the EuroQol (Appendix I), and to use this information to estimate the quality adjusted life years (QALYs) generated during the 28 days after admission.

Rapid molecular and near patient diagnostic tests result in an improvement in quality-of-life, as measured by the EuroQol, which arises from streamlining of antibiotics and earlier discharge into the community.

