#### 6.2.9 Quality of Life assessment (Days 7 and 28)

All patients will be assessed by the EuroQol (Appendix I) on Days 7 and 28, and the results recorded in the CRF. Patients who have been discharged will be assessed by post using a questionnaire, or by a simple telephone interview.

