#### 7 and 28 day follow up questionnaires for those who have been discharged.

- 1. There is an additional questionnaire to be completed if the subject as been discharged.
- 2. If a proxy is to be used then the same proxy should be used to complete all questionnaires for the subject if possible.
- 3. The research nurse should obtain the proxy's address and post the questionnaire to them with a stamped addressed envelope before the 7 or 28-day time point.
- 4. At the 7 day time point the respondents should be sent the appropriate EuroQol (either selfcomplete or proxy). Those who require it should have a telephone interview (see point C above)
- 5. At 28 days all discharged subjects should be sent appropriate 28 day questionnaire (either selfcomplete or proxy). Again, those who would be unable to complete a questionnaire should have a telephone interview (see point C above).
- 6. Non-responders should be sent another form and reminder 7 days after this period.

Version 1 18th May 2005

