#### HOSPIAL HEADED NOTEPAPER

#### Day 28 postal questionnaire

# A RANDOMISED CONTROLLED TRIAL TO EVALUATE IMPACT OF DIAGNOSTIC TESTING FOR INFLUENZA, RESPIRATORY SYNCYTIAL VIRUS AND STREPTOCOCCUS PNEUMONIAE INFECTION ON THE MANAGEMENT OF ACUTE ADMISSIONS IN THE ELDERLY AND HIGH-RISK ADULTS.

Name	Study Number
Admission date//	Discharge date//
Date of 28 days from admission date	//

During your recent stay in hospital you kindly agreed to take part in the above study. As part of this research we would like to ask you a few questions about any health care you have received since you were discharged from hospital

We would also like to ask you a few simple questions about your health today.

**Question 1.** Firstly, we would like to ask you if any of the following health care professionals have visited you in your own home since you were discharged from hospital? For each type of person, please tick the box if you saw this health care professional and tell us how many times you saw this person. Remember, here we are only interested in health care you have received in your own home.

1	GP	How many times?
$\square_2$	District nurse	How many times?
3	Practice nurse	How many times?
4	Other nurse	How many times?
5	Home care worker/ home help	How many times?
6	Other person (please specify)	How many times?
7	Other person (please specify)	How many times?
8	Other person (please specify)	How many times?

**Question 2.** We would now like you to think of any health care professionals that you might have seen outside your own home since you were discharged from hospital. For each type of person, please tick the box if you saw this health care professional and tell us how many times you saw this person. Remember, here we are only interested in visits you have made to receive healthcare outside your home.

1	Hospital doctor in outpatients department	How many times?
$\square_2$	GP	How many times?
3	Practice nurse	How many times?
4	Other nurse	How many times?
5	A&E department	How many times?
6	Other (please specify)	How many times?
7	Other (please specify)	How many times?
8	Other (please specify)	How many times?

**Question 3.** Since your discharge from hospital have you had any extra medicines prescribed for you?

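### Appendix I forms do not keep to the plan's measurement times: resource questions have no Day 28 end, and the Day 7 EuroQol can be completed before or well after Day 7

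*Protocol*

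**What the plan says.** **Intended times.** Section 2.1 sets out to "estimate the quality adjusted life years (QALYs) generated during the 28 days after admission" and to assess "costs post-discharge up to a maximum of 28 days after admission". Section 6.2.9 fixes the follow-up times: "All patients will be assessed by the EuroQol (Appendix I) on Days 7 and 28". The schedule of assessments allows one day either side of Day 7 and two days either side of Day 28. Section 4.1 defines post-discharge resource use as running from discharge until Day 28, and section 6.2.4 applies the same 28-day limit to GP consultations and hospital follow-up.

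**The forms and instructions in Appendix I.**

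- The 7-Day follow up EuroQol sheet says, for discharged patients: "ENSURE PATIENT HAD SELF COMPLETE EUROQOL GIVEN TO THEM ON DISCHARGE". The form is posted only if that was missed. The 28-Day sheet carries the same instruction.
- The section on 7 and 28 day follow-up questionnaires for discharged patients says something else: "At the 7 day time point the respondents should be sent the appropriate EuroQol", with a parallel rule at 28 days. Proxy forms are to be posted before the time point. For late responders: "Non-responders should be sent another form and reminder 7 days after this period".
- The Day 7 postal form asks about health on the day of completion and adds "We would be grateful if you could complete this questionnaire as soon as possible". The Day 7 proxy form says the same. Both ask for the completion date; neither prints a target date.
- The Day 28 postal form and the 28-day telephone script ask about "any health care you have received since you were discharged from hospital". Both print the Day 28 date in the header, but no question refers to it. As shown, neither has a field for the date of completion or interview.

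**The concern.** Cost per QALY is one of the two main economic outcomes in section 7.5.2, and both its parts are defined over a fixed 28-day period. If a form does not state the period, the answer covers whatever period the return date produces. For resource use, no later analysis can recover a cut-off that was never put to the respondent, least of all when the return is undated. For the EuroQol, a value labelled Day 7 may describe an earlier or later stage of recovery. How early it can be completed depends on the discharge date, and length of stay is itself an outcome that the rapid tests are meant to change. The Day 7 timing error could therefore differ between groups.

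**Working it through.** The protocol gives no figure for this point, so there is nothing to reproduce. The check compares the instructions and then sizes the effect under stated assumptions.

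**1. Resource window.** Let L be the day of discharge (before Day 28) and R the day the form is answered; both are assumed. The planned window is 28 − L days. The window the form asks about is R − L days. The excess is (R − L) − (28 − L) = R − 28, which does not contain L.

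| L | Planned days | Days asked about if R = 35 | Excess | Ratio |
|---|---|---|---|---|
| 3 | 25 | 32 | 7 | 32/25 = 1.28 |
| 7 | 21 | 28 | 7 | 28/21 = 1.33 |
| 14 | 14 | 21 | 7 | 21/14 = 1.50 |

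R = 35 is when the second form goes out if the 7 days are counted from Day 28. An answer on Day 42 after discharge on Day 7 gives 35/21 = 1.67. These are ratios of days covered, not of cost. A form answered before Day 28, as an early-posted proxy form could be, covers too few days.

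**2. When a Day 7 value can arise.**

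- Form handed over at discharge on, say, Day 3 and completed at once: Day 3.
- Proxy form posted before the time point and completed on receipt: possibly before Day 7.
- Form sent on Day 7 and returned after the reminder: about 7 + 7 = Day 14.

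Day 3 and Day 14 both lie outside the Day 6 to 8 window.

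**3. Weight in the QALY.** Assume linear interpolation over Days 0, 7 and 28.

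- Day 7 weight: 7/2 + 21/2 = 14 days, half of 28.
- Day 28 weight: 21/2 = 10.5 days, 37.5% of 28.
- Maximum 28-day QALY: 28/365 = 0.0767.
- An assumed 0.1 utility error at Day 7: 0.1 × 14/365 = 0.0038, or 5% of the maximum. At Day 28: 0.1 × 10.5/365 = 0.0029, or 3.75%.

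**4. Illustrative recovery.** Assume utility u(t) = 0.7 − 0.4·exp(−t/τ), with τ of 5, 10 and 20 days. The change in the interpolated QALY, against values taken on the right days, is:

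| Mistimed value, analysed as if on time | τ = 5 | τ = 10 | τ = 20 |
|---|---|---|---|
| Day 7 form completed on Day 3 | −10.1% | −9.0% | −6.6% |
| Day 7 form completed on Day 14 | +6.2% | +9.2% | +8.8% |
| Day 28 form completed on Day 35 | +0.1% | +0.8% | +2.3% |

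**5. What the recorded date recovers.** Take τ = 10, with u(0) = 0.3000, u(3) = 0.4037, u(7) = 0.5014 and u(28) = 0.6757.

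- On-time area: 3.5 × (0.3000 + 0.5014) + 10.5 × (0.5014 + 0.6757) = 15.16 days.
- Day 3 value placed on its true date: 1.5 × (0.3000 + 0.4037) + 12.5 × (0.4037 + 0.6757) = 14.55 days, or −4.1% instead of −9.0%.

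Using the date roughly halves the error in this example. The rest remains because the Day 7 state was never observed.

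**The case against.** Several points on the other side stand.

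- The hand-over at discharge is not uniform. The data-collection procedure sends forms at the time point, and if that is followed, a request for prompt completion usefully limits delay. The document contradicts itself; it does not prescribe early completion throughout.
- The form handed over may be the general Self completion Health Questionnaire. That form lacks the request for promptness and has a date field. It still asks about the respondent's health that day and prints no target date, so early completion remains possible.
- The request for promptness is on the Day 7 forms only, and those are dated. Using the recorded dates is an analysis detail that may sit in a statistical analysis plan not shown here.
- Sections 4.1 and 6.2.2 plan a reminder call on Day 28, so not every reminder comes a week late.
- The 28-Day follow up EuroQol sheet has a date of interview, which may date some Day 28 responses, particularly telephone ones. The postal form shows no such field.
- The telephone option in the health-economic data procedure is for patients who cannot complete the form themselves. It does not conflict with the postal procedure.

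A reader might infer that both errors work against the rapid tests, because earlier discharge would mean more uncapped time and an earlier Day 7 reading. The documents do not support this. The excess resource time is R − 28 whatever the discharge day, so a shorter stay adds none, and the relative excess is larger after later discharge. For the EuroQol, early completion lowers and reminder-driven completion raises a recovering patient's QALY. The balance between groups is not known.

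**Conclusion.** The point holds as a mismatch between the plan's measurement times and its own forms. It does not show that every patient is measured at the wrong time, nor a bias in a known direction.

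The resource questions are the firmer part. Followed as written, they collect care outside the stated 28 days whenever the answer comes late: 7 days too many at Day 35. On the postal form nothing visible allows a correction. The EuroQol part is a contradiction over dispatch together with Day 7 forms that set no target date, so some Day 7 values may come from before Day 7 or from about Day 14.

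The 0.0038 QALY is a per-patient figure from an assumed 0.1 error under linear interpolation, not a difference between groups. The 7 to 10% and 6 to 9% shifts rest on an assumed recovery curve and on analysing the value as if it were on time. The protocol gives no share of patients affected and no return dates, so the effect on cost per QALY cannot be sized.

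**What to change.** 1. Make the section on follow-up questionnaires for discharged patients and the 7-Day and 28-Day follow up EuroQol sheets give one dispatch procedure, covering proxies as well.
2. Print a target date on every follow-up form, for example *Please complete this form on [date]*, in place of the undated request for promptness on the Day 7 forms.
3. Reword the resource questions on the Day 28 postal form and telephone script to run *from your discharge up to and including [the Day 28 date printed on this form]*.
4. Add a completion date to the Day 28 postal form and an interview date to the telephone script.
5. Compute QALYs from actual completion dates.

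The cost is reprinting and a short instruction to the research nurses. A few returns may be lost if forms are no longer handed over in person; the Day 28 reminder call already planned limits this for the second form. Because this protocol version is dated November 2007, within the third enrolment season, forms already returned cannot be re-asked. For those, use the recorded Day 7 dates and, if it was logged, the date of receipt as the latest possible completion date of the Day 28 form.
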